### **Data Management**

The Applied Health Research Centre (AHRC) of the Keenan Research Centre, Li Ka Shing Knowledge Institute of St. Michael's Hospital, University of Toronto, will serve as the data management centre under the direction of [name], Director of the AHRC (<http://www.stmichaelshospital.com/research>). AHRC employs state-of-the art web-based data

## **Trial title: Optimizing Early Child Development in the Primary Care Practice Setting: Pragmatic Randomized Trial of Iron Treatment for Young Children with Non-anemic Iron Deficiency (OptEC)**

management software: Medidata RAVE™ (5.6.3). RAVE™ is a secure encrypted web-based clinical trial data management system which is fully configurable and incorporates sophisticated data validation rules to ensure high quality data is captured. RAVE™ is a web-based application allowing for remote web-based data entry directly from the participating practice sites, and facilitates real-time data access. Data from the *TARGet Kids!* initiative, launched in September 2008, has been entered into a RAVE™ database and will be leveraged for this study. The licensing fee has been paid through previous *TARGet Kids!* related grants.

### **Trial Monitoring**

A Data Monitoring Committee is not deemed necessary, as the experimental intervention (oral iron treatment 6 mg elemental iron/kg/day given once daily or in 2 or 3 divided doses daily for four months plus dietary counseling) is standard of care for children in the same age group with IDA and the side effect profile is well known. In the current study of children with NAID, similar side effects are expected and will be collected. There will be no criteria or plans for early trial termination.

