**Interventions** – Children with NAID will be randomized to receive either oral iron treatment 6 mg elemental iron/kg/day or placebo (equivalent volume) once daily or bid or tid, at the discretion of the prescribing study doctor based on the patient's tolerance and preference, for four months. Dietary advice will be provided to both the groups. Dietary advice will include recommendations regarding maximum daily cow's milk intake, varied solid food intake including high iron containing foods, and avoidance of foods which reduce iron absorption. As this is a pragmatic trial, no specific strategies will be introduced to improve adherence. To monitor adherence at the end of the trial, parents will be asked to return bottles and the amount of iron administered will be calculated based on the volume of solution remaining. No specific criteria will be developed for discontinuation or modification of the interventions, as the dose of iron is within the safe and recommended dosages for children.

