**Investigational Agent**

Active Arm: Ferrous Sulfate Oral Solution Drops USP (brand Fer-In=Sol by Mead Johnson); Strength: 75mg Ferrous Sulfate/mL = 15mg Fe++/mL; NPN # 00762954; Commercial supply donated in kind by Mead Johnson. Blinded over-labeling will be done by the SickKids Research Support Pharmacy.

Placebo Arm: The placebo is developed by the Hospital for Sick Children Compounding Pharmacy. Contains preserved water (preserved with sodium benzoate), simple syrup NF, denatonium benzoate (for bitter/medicinal taste) and food colouring (see detailed worksheet); similar in colour and taste to active; packaged in 50mL bottles identical to active Fer-in-Sol (empty bottles donated in kind by Mead Johnson).

**Trial title: Optimizing Early Child Development in the Primary Care Practice Setting: Pragmatic Randomized Trial of Iron Treatment for Young Children with Non-anemic Iron Deficiency (OptEC)**

Both active and placebo arms will be packaged in identical bottles with blinded labels. A participant information sheet that contains information regarding the study drug will be provided to parents who agree to participate in the trial.

**Outcomes** – A complete course of iron therapy is 4 months. Changes in developmental and hematologic status may be expected within this time frame. Outcomes will be measured at two time periods: baseline and 4 months after enrollment. The primary outcome will be the developmental score using the Mullen Scales of Early Learning (MSEL). The secondary outcomes will include the behavior measure (Early Childhood Behavior Questionnaire) and two laboratory measures (hemoglobin and serum ferritin levels). The analysis metric will be the mean difference in outcome between the treatment and control groups at 4 month follow up, adjusting for the baseline measures.

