**Participant Timeline**

**Trial title: Optimizing Early Child Development in the Primary Care Practice Setting: Pragmatic Randomized Trial of Iron Treatment for Young Children with Non-anemic Iron Deficiency (OptEC)**

Participants will be assessed at two time periods: baseline and four months after the baseline visit. The baseline assessment will be carried out in two steps. Step 1: The baseline TARGeT Kids! Data collection; Step 2: According to the lab test results those who agree to participate in the OptEC trial will be asked to come back to the physicians office where the developmental testing will be performed. Data (questionnaires, physical measurements, developmental testing and laboratory testing) will be collected at both the baseline and follow-up periods. There is no requirement for a run-in period or washout period.

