**Data Collection Methods**

Questionnaire data and physical measurements will be collected by the Research Assistants who are embedded in the practices. The Research Assistants have been trained to ensure accuracy of data collection and the questionnaires have been extensively pilot tested. The TARGeT Kids! Health and Nutrition Questionnaire will be used to collect data only at baseline, a follow-up questionnaire will be used at the follow-up visit and the ECBQ will be used both at baseline and

**Trial title: Optimizing Early Child Development in the Primary Care Practice Setting:  
Pragmatic Randomized Trial of Iron Treatment for Young Children with Non-anemic Iron Deficiency (OptEC)**

follow-up visit. Blood work will be obtained by trained personnel according to the arrangements established at each of the practice sites; for example at some sites the Research Assistant is also a trained Phlebotomist and at some sites the clinic Nurse performs phlebotomy. Blood testing will be performed once during the TARGet Kids! visit and then after four months during the follow-up visit. The Research Assistant is responsible for ensuring the blood is delivered to Mount Sinai Services (MSS) for laboratory testing. MSS provides customized laboratory and research services to pharmaceutical and biotech companies, and researchers

(<http://www.mountsinaiservices.com/pages/Home>). Laboratory results are sent electronically to the data management centre (see next section) as well as faxed to the practicing physician who is responsible for communicating the results to the participants. Children eligible for the randomized trial will return to the physician's office where the Mullen Scales of Early Learning will be administered by a trained psychometrist under the supervision of one of the co-investigators who is a developmental psychologist ([name]). This will take approximately 30-40 minutes. At the 4 month follow up visit, the Research Assistant is responsible for ensuring that the questionnaires, physical and laboratory measures are completed. The psychometrist will complete the MSEL.

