**Probable lost to follow-up patients**

**Children who fail to show-up for their 4 month follow-up visit will be contacted initially on alternate days up to a period of one month and then on a monthly basis until the end of the trial period (4 years) by the RAs over telephone.**

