**Adverse event reporting**

All adverse events will be reported to the Hospital for Sick Children Research Ethics Board according to the Hospital for Sick Children's adverse event reporting requirements. All adverse drug reactions to the study medication will be reported to Health Canada within 15 calendar days or for death or life-threatening events, within 7 calendar days. In the latter case, a follow-up

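### Side effects are to be collected, but the plan describes no instrument that asks about them, schedules one on-treatment contact at month 4, and plans no comparison of harms between arms

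*Combined protocol and SAP*

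**What the plan says.** Trial Monitoring explains why no Data Monitoring Committee is planned and then states: "In the current study of children with NAID, similar side effects are expected and will be collected".

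The visit schedule is short. Participant Timeline says "Participants will be assessed at two time periods: baseline and four months after the baseline visit", and the Outcomes paragraph agrees: "Outcomes will be measured at two time periods: baseline and 4 months after enrollment". Telephone follow-up during or after treatment is planned only where the final visit is missed: "Children who fail to show-up for their 4 month follow-up visit will be contacted initially on alternate days".

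On instruments, Data Collection Methods says that "a follow-up questionnaire will be used at the follow-up visit", without giving its items, and that at month 4 "the Research Assistant is responsible for ensuring that the questionnaires, physical and laboratory measures are completed". The measures that are described are the family questionnaire, the behaviour questionnaire (ECBQ), laboratory tests, physical measurements and the MSEL.

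The Outcomes paragraph names the MSEL as primary and the ECBQ, hemoglobin and ferritin as secondary. Statistical Analysis compares developmental and hematologic measures between the randomized arms. Neither mentions side effects. Sub-study #2 adds growth and hematologic outcomes only.

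Adverse event reporting sends all adverse events to the Research Ethics Board and adds: "All adverse drug reactions to the study medication will be reported to Health Canada within 15 calendar days". The limit is 7 days for death or life-threatening events. Under Interventions, the daily dosing frequency is set "at the discretion of the prescribing study doctor based on the patient's tolerance and preference".

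**The concern.** The protocol commits to collecting side effects but gives no means of doing so systematically. Between the first dose and month 4, an event becomes known only if a family or a treating physician volunteers it. At month 4 it becomes known only if someone happens to ask or the parent happens to mention it.

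The section on the pragmatic-explanatory continuum says that the trial's main purpose is to inform clinical decisions. The decision here is whether to treat children found by screening who are not anemic, and that needs an estimate of harm beside the estimate of benefit. Trial Monitoring expects side effects in these children to resemble those known in iron deficiency anemia. A blinded placebo comparison is the right tool to examine that expectation, but the plan neither standardizes the data nor specifies the comparison.

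**Working it through.** **Is there a figure to reproduce?** No. The documents state no expected side-effect rate, precision or power for harms. The point rests on the text; the arithmetic below only shows scale.

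**Passages set side by side**

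| Needed to estimate harm | What the plan provides |
|---|---|
| A stated intention | Yes (Trial Monitoring) |
| A described question or form | None described; month-4 follow-up questionnaire listed without content |
| Scheduled contact on treatment | One, at month 4 (Participant Timeline; Outcomes) |
| Telephone contact | Only after a missed month-4 visit |
| A safety outcome | None (Outcomes) |
| A by-arm comparison | None (Statistical Analysis; Sub-study #2) |
| Start of the 15- and 7-day clocks | Not stated (Adverse event reporting) |

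Returned bottles, described under Interventions, show how much was given but not why dosing stopped.

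**Length of recall.** Four months is 4 × 30.44 = 121.8 days. An event just after the first dose can precede the next scheduled contact by about 122 days.

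**Effect of incomplete capture (illustration).** Sample Size randomizes 180 children, so n = 90 per arm. *Assumed*, not in the documents: true rates p1 = 30% on iron and p0 = 15% on placebo, and a fraction c of events captured equally in both arms. The observed rates are a = c·p1 and b = c·p0. Then

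- observed difference = c(p1 − p0)
- SE = √[a(1 − a)/90 + b(1 − b)/90]
- 95% CI half-width = 1.96 × SE
- approximate two-sided 5% power = Φ(difference/SE − 1.96)

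At full capture: SE = √[(0.21 + 0.1275)/90] = 0.0612, half-width = 12.0 points, power = Φ(0.15/0.0612 − 1.96) = Φ(0.49) = 69%.

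| Captured | Observed rates | Difference | Half-width | Power |
|---|---|---|---|---|
| 100% | 30% v 15% | 15.0 points | 12.0 | 69% |
| 50% | 15% v 7.5% | 7.5 points | 9.2 | 36% |
| 30% | 9% v 4.5% | 4.5 points | 7.3 | 23% |

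A second assumed pair, 15% v 5%, gives the same pattern with the same formulas: a 10-point difference with 62% power at full capture, and 5 points with 34% power at half capture.

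**Best case for rare events.** If every child in a 90-child arm is asked and none has a given event, the one-sided 95% upper bound is 1 − 0.05^(1/90) = 3.3%. That bound is valid only if all were asked.

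**The case against.** The strongest reply is that the protocol is not silent on safety. The month-4 follow-up questionnaire may contain side-effect items. The trial runs in the children's own primary care practices. Unblinding Procedures routes deterioration or severe, persistent side effects from the treating physician to the investigators. Premature Withdrawal Criteria lists safety events. All adverse events go to the ethics board, and Quality Assurance audits adverse-event reporting in at least 10% of records. Sparse follow-up is also a deliberate pragmatic choice.

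Much of this stands, and it limits what can be claimed:

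- A reader might infer that no form asks about side effects. That cannot be verified, because the follow-up questionnaire's content is not given and the study schematic is not shown. The text supports only that none is described as asking.
- A reader might infer that the decision against a committee depends on collecting side effects. It does not. The stated reasons are that the regimen is standard care in iron deficiency anemia and that its side-effect profile is well known.
- A reader might infer that the 15- and 7-day deadlines would be missed, by comparing them with a four-month gap. That holds only if the clocks run from onset, and the protocol gives no starting point. Severe events also have the physician route, so it is fair to say only that between-visit reports are unsolicited.
- The ECBQ's two-week window concerns the rating of everyday behaviours. It sets no standard for recalling drug reactions.
- Setting the dosing frequency by tolerance does not itself require a research visit.

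What the reply does not answer is that none of these routes asks every family the same question. Even a suitable item in the follow-up questionnaire would leave the analysis without a comparison.

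**Conclusion.** The point holds as a gap in how harms are elicited and analysed. As written, harms data would come from unsolicited reports between visits or from recall over about four months, and no by-arm comparison is planned. The randomized, blinded, placebo-controlled design would then give no planned estimate of harm in non-anemic children.

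Under-counting is a likely risk, not a demonstrated fact, and its size is unknown because the documents give neither event rates nor a capture fraction. If capture is incomplete but equal in the two arms, both counts and the risk difference shrink in proportion. Under the assumed 30% v 15% at 90 per arm, the difference falls from 15 points to between 4.5 and 7.5, and power from 69% to between 23% and 36%. Those figures show direction and scale only. Unequal capture could bias the difference either way.

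The change is worth making because it is cheap and adds to what the trial can conclude. It does not threaten the primary developmental comparison.

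**What to change.** 1. **Data Collection Methods:** add a fixed side-effect checklist, worded identically for both arms, with a stated recall period, asked by the blinded Research Assistant at the month-4 visit. If the follow-up questionnaire already contains such items, say so and describe them. For children who miss the visit, the telephone contacts already planned could use the same checklist.
2. **Statistical Analysis:** add a descriptive table by randomized arm giving children with at least one event, each event type, and stopping of study product because of side effects, with risk differences and 95% confidence intervals in all randomized children. Show how many answered the checklist. At the upper end of the protocol's 0–20% drop-out, 0.20 × 180 = 36 children could lack it.
3. **Adverse event reporting:** state when the 15- and 7-day clocks start.
4. **Reconcile** Interventions, which says that no specific criteria for discontinuing or modifying treatment will be developed, with Premature Withdrawal Criteria, which lists some, so that reasons for stopping are recorded on one basis.

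One brief early on-treatment call with the same checklist is optional. It would shorten recall at the cost of about 180 calls and slightly less pragmatic follow-up in both arms. A series of monthly calls is not needed and would fit poorly with the deliberately light follow-up.

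Without the call, the cost is a short form, a few minutes of Research Assistant time per child and one table.

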### **SUB-STUDIES OF THE OptEC TRIAL:**

[name] is a Pediatrician trained in Bangladesh and currently a PhD student in the Clinical Epidemiology and Health Services Research program in the University of Toronto, Department of Health Policy, Management and Evaluation. [name] is her supervisor. In accordance with the Department of Health Policy, Management and Evaluation rules for the PhD program she has submitted a proposal for her PhD thesis and the department has accepted her proposal. Among the three projects she will carry out for her PhD thesis two of them will be undertaken as sub-studies of the OptEC trial. Members of the thesis committee and co-investigators of the OptEC trial have approved the sub-studies for the PhD student.

#### **Sub-study #1: Internal pilot study to estimate the sample size for the OptEC trial.**

The estimates we have used for the calculation of sample size for the multi-centre OptEC trial are based on literature review. It has been shown that sample size estimates based on literature review are likely to be considerably less than the true values because the literature tends to report more homogenous cases series than will be entered in a large clinical trial, especially an efficient one with inclusive entry criteria . Furthermore prior estimates are often obtained from trials that may have different study conditions to the trial, for example different patient types, small number of centres, different treatment duration . Thus the prior estimates obtained from these studies may not be representative of the current randomized trial. These potential problems can be overcome by the use of an internal pilot study which forms an integral part of the trial itself and not a separate study. The methodologic issues associated with internal pilot studies are described in the literature of the references.

#### Objectives of the internal pilot study:

1. To obtain a reliable estimate of the variance ( $\sigma^2$ ) of the child development scores
2. To obtain the baseline to 4 month correlation coefficient of the developmental scores based on actual data from patients entered in the trial
3. To recalculate the sample size of the trial using the estimates of the internal pilot
4. To determine pre-randomization feasibility issues

**Trial title: Optimizing Early Child Development in the Primary Care Practice Setting: Pragmatic Randomized Trial of Iron Treatment for Young Children with Non-anemic Iron Deficiency (OptEC)**

**Sample size:**

The minimum size for an internal pilot study should be 10 or more patients per intervention group. It has been shown that the larger the size of the internal pilot the more the accurate will be the estimates and so more appropriate will be the recalculated sample size . Thus based on these facts the sample size may be recalculated after 30 participants have been enrolled in the randomized trial.

In order to recalculate the sample size for the OptEC trial using the estimates of the internal pilot study, we will not need to break the randomization code. As discussed with the study statistician this methodology is in alignment with proper conduct of clinical trials. None of the investigators will be unblinded to subjects' group allocation.

**Sub-study #2: The effectiveness of oral iron therapy in improving the growth and haematological outcome of pre-school children with non-anemic iron deficiency (NAID): A randomized trial.**

**Research Question in PICOT format:**

P = Pre-school children aged 18-36 months identified as having NAID (defined as serum ferritin <12 µg/L and hemoglobin >110 g/L) enrolled in the TARGet Kids! Research Network program

I = Oral iron (6mg elemental iron/kg/day in two divided doses) plus parental dietary counselling

C = Placebo plus parental dietary counseling

O = Hematological indices (serum ferritin and hemoglobin level), Growth parameters (weight and height)

T = Four (4) months

**Objective of the study:**

The objective is to evaluate whether oral iron therapy given to pre-school children (18-36 months) with NAID affects their hematological and growth outcome by comparing those receiving either oral iron therapy or placebo for four months (with both groups receiving parental dietary counseling).

**Sample size:**

The sample for this sub-study will be the first 40 NAID children enrolled in the randomized trial. Based on previous literature it has been shown that 1.2 cm improvement in children's height is a clinically significant improvement . Thus it has been found that a sample of 40 will have 90% power to detect a difference of 1.2 cm improvement in height (with a SD=1), at 0.05% significance level.

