**Analysis:**

An analysis of variance using multiple linear regression procedure to examine the association between the post-intervention differences in hematological and growth parameters of the two intervention groups will be carried out after adjusting for the baseline growth and serum ferritin measurements.

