## **Trial title: Optimizing Early Child Development in the Primary Care Practice Setting: Pragmatic Randomized Trial of Iron Treatment for Young Children with Non-anemic Iron Deficiency (OptEC)**

Group allocation for the first 40 subjects of the OptEC trial will be identified only for the hematological and growth parameters (secondary outcomes) for the analysis of the sub-study. This un-blinding will only be made known to co-investigator (KA) who will no longer be involved with the ongoing conduct of the trial. Group allocation for the primary outcome of the OptEC trial (developmental scores) will remain concealed and will not be analyzed for this sub-study. This methodology has been verified and accepted by the study statistician and other members of the OptEC trial team members.

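### Growth is compared by arm only in the first 40 children although all are measured, and hemoglobin and ferritin are analysed twice with no statement of which result is definitive

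*Combined protocol and SAP*

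**What the plan says.** **Sub-study #2.** The sample is defined under Sample size: "The sample for this sub-study will be the first 40 NAID children enrolled in the randomized trial". The outcomes in the PICOT list are "Hematological indices (serum ferritin and hemoglobin level), Growth parameters (weight and height"). The comparison is by arm: "Group allocation for the first 40 subjects of the OptEC trial will be identified only for the hematological and growth parameters (secondary outcomes"). The Analysis paragraph plans a regression of "the post-intervention differences in hematological and growth parameters of the two intervention groups will be carried out after adjusting for the baseline growth", with baseline ferritin as a further covariate. It gives no test level and does not name baseline hemoglobin as a covariate. The only significance level in the sub-study is in the height calculation: "a sample of 40 will have 90% power to detect a difference of 1.2 cm improvement in height (with a SD=1), at 0.05% significance level".

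**Main trial.** The Outcomes paragraph lists the behavior questionnaire and "two laboratory measures (hemoglobin and serum ferritin levels") as secondary outcomes. Growth is not listed there, although Sub-study #2 calls it a secondary outcome. Statistical Analysis plans an ANCOVA of the developmental and hematologic measures in all randomized NAID children by intention to treat, which includes the first 40. It does not mention growth.

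**Data collection.** Participant Timeline has physical measurements taken at both baseline and follow-up. Data Collection Methods says that at the 4-month visit "the Research Assistant is responsible for ensuring that the questionnaires, physical and laboratory measures are completed". Neither section restricts this to the first 40 children.

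**The concern.** There are two separate consequences.

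1. **Growth.** The data for a full-sample comparison of height and weight will exist, but the only treatment comparison specified uses 40 children. An estimate from 40 children is about half as precise as the trial could give at no extra burden to families or sites.

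2. **Hemoglobin and ferritin.** These are compared by arm in the first 40 children and again at the end in a set that contains those 40. No section ranks the two analyses, calls the first preliminary or divides the significance level between them. No early stopping is planned (Trial Monitoring), so the second analysis will follow whatever the first shows. The two models also adjust for different covariates. If the results differ, the protocol has no rule for which one stands, and an iron-status effect has two chances to be declared.

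**Working it through.** **Inputs**
- Sub-study #2, Sample size: 40 children (20 per arm), height difference 1.2 cm, SD 1, power 90%, level printed as 0.05%.
- Sample Size (main trial): 150 evaluable children, 180 randomized, significance level 5%. This 5% is stated only for the Mullen score.
- Assumed: two-sided tests, because the documents do not state sidedness; all 40 children contribute data.

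**1. The sub-study's own power figure**

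Power = Φ(δ/SE − z), with SE = √(2/20) = 0.316 and δ/SE = 1.2/0.316 = 3.79.

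| Two-sided level | z | Power (normal) | Power (t) |
|---|---|---|---|
| 0.05%, as printed | 3.48 | Φ(0.31) = 62% | 51% |
| 5% | 1.96 | Φ(1.83) = 97% | 96% |

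Neither level gives 90% with 20 per arm. A 1% level gives 88.9% by the normal formula, but no section states 1%. A total of 40 is recovered by taking 5%, which needs 16 per arm by the t distribution (power 90.7%), and then allowing 20% loss: 32/0.8 = 40. The sub-study does not state that allowance. The printed 0.05% is therefore most likely a slip for 5% or 0.05.

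**2. Growth: 40 children against about 150**

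SE = √(4/N) with SD 1. Difference detectable with 90% power = (1.960 + 1.282) × SE.

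| N | SE (cm) | 95% half-width, 1.96 × SE (cm) | Detectable difference (cm) |
|---|---|---|---|
| 40 | 0.316 | 0.62 | 1.03 |
| 150 | 0.163 | 0.32 | 0.53 |

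The ratio of standard errors is √(40/150) = 0.516, about 52%.

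**3. Hemoglobin and ferritin: two nested tests of one outcome**

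With no treatment effect, the two test statistics are approximately bivariate normal with correlation √(40/N). The chance of at least one false positive is 1 − P(|Z1| ≤ c1 and |Z2| ≤ c2).

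| First level | Final level | N = 150 (correlation 0.516) | N = 180 (correlation 0.471) |
|---|---|---|---|
| 5% | 5% | 9.03% | 9.15% |
| 0.05% | 5% | 5.03% | 5.03% |

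Simulation with 400,000 runs gave 8.98% and 9.13% for the first row. Two independent tests would give 1 − 0.95² = 9.75%, so the overlap reduces the inflation only a little. If only the full-sample test counts, the figure is 5.0%.

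**The case against.** **The level is not known to be 5% at both looks.** This stands. The only level printed for Sub-study #2 is 0.05%, and no section sets one for hemoglobin or ferritin. A reader might take 9% as an established property of the plan. It is conditional, and the documents allow anything from 5.03% to 9.15%. The upper end is the more plausible because 0.05% does not fit the stated power.

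**The full-sample analysis already leads.** Statistical Analysis calls its ANCOVA primary, and the 40-child work is labelled a sub-study. This has some force, but in context the word primary separates the baseline-adjusted model from the version with extra covariates. It does not rank the ANCOVA against Sub-study #2.

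**These are secondary outcomes and nothing can stop early.** This is true and limits the weight of the point. The safeguards under Sub-study #2 (one co-investigator unblinded, who then leaves trial conduct; developmental scores kept concealed) protect blinding and the primary outcome. They do not address repeated testing, and the trial's hypothesis does name laboratory outcomes.

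**Forty children are enough for 1.2 cm.** At 5% the power is about 97%, so the sub-study meets its own target. The gain for growth is in precision and does not repair inadequate power.

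**Stronger readings the text does not support.** A reader might infer that growth data beyond the first 40 will be discarded. The documents only omit a full-sample analysis, and the Outcomes list is not worded as exhaustive. A reader might expect two conflicting publications, but no separate publication of the sub-study is promised. A reader might combine the two outcomes into a 17% error rate: 1 − (1 − 0.09)² = 0.17. That assumes independence and mixes in multiplicity across outcomes, which already gives 9.75% with a single look.

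**Conclusion.** The point holds as a matter of specification. Growth is measured in everyone, but a treatment comparison is specified only for the first 40. With about 150 evaluable children the standard error falls to about 52%, and the height difference detectable with 90% power falls from 1.03 to 0.53 cm. This rests on the sub-study's SD of 1, a two-sided 5% test and no allowance for baseline adjustment.

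For hemoglobin and ferritin, two overlapping analyses have no stated order of precedence. The chance of a false positive at either look is about 9% per outcome if both use two-sided 5%, and 5.03% if the printed 0.05% governs the first. That printed level is inconsistent with the stated 90% power and needs correcting in any case.

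The primary Mullen comparison is untouched, because the sub-study does not analyse it by arm. The change is worth making because it is cheap, but the trial's main conclusion does not depend on it.

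**What to change.** 1. **Growth.** Add to Statistical Analysis a baseline-adjusted comparison of height and weight in all randomized children with 4-month data, and list growth under Outcomes so that the sections agree on its status.
2. **Hemoglobin and ferritin.** State that the full-sample ANCOVA is the only hypothesis test for these two outcomes. Report the first-40 results as preliminary estimates with confidence intervals. This returns the error rate to 5.0% per outcome. A formal alpha-spending boundary would be disproportionate for secondary outcomes in a trial with no early stopping.
3. **Sub-study #2, Sample size.** Correct the significance level, state whether the test is one- or two-sided, and restate the power to match. If an allowance for loss was built into the 40, say so.

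The cost is a few sentences and one additional analysis of data already collected. The sub-study can proceed as planned. The downside is that it can no longer claim significance for hemoglobin or ferritin on its own.
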